Secondary Aim: Examine the influence of menthol flavor on the effects of nicotine (freebase vs salt) stimulation, craving reduction, and alleviation of nicotine withdrawal. Participants will rate nicotine withdrawal and stimulation using the Revised DEQ and cigarette craving using the gLMS.

Exploratory Aim: Examine nicotine delivery following exposure to nicotine salt vs freebase nicotine exposure in combination with flavors (tobacco or menthol) by measuring saliva nicotine levels 5 min prior and 5, 15, 30, 45, and 55 minutes after nicotine and flavor exposure via e-cigarettes

K01 metabolism study

Eighty-Five African Americans (43 F, 42 M) who smoke and have experience with e-cigarettes will participate in a double-blind, randomized, cross-over study across two experimental sessions. Following overnight abstinence from combustible tobacco products (CO≤10 ppm), participants will be randomly assigned to receive an e-cigarette with menthol flavor or control tobacco flavor (both in a concentration of 5% nicotine) on two separate days. Each session will consist of 1 puffing bout (10 puffs, 3 sec each puff, 30 sec puff interval) followed by 2 hours of abstinence, then 60 minutes of ad libitum e-cigarette use. The specific aims are:

Aim 1: Investigate the relationship of menthol flavor (vs tobacco flavor) and nicotine metabolite ratio (NMR) on nicotine pharmacokinetics and subjective effects during directed e-cigarette administration in African Americans who smoke. We hypothesize that during the menthol exposure session participants will have higher plasma nicotine levels compared to the tobacco flavor exposure session. We hypothesize that NMR is negatively associated with nicotine plasma levels during the tobacco flavor exposure sessions. Lastly, we hypothesize that participants will have a larger reduction of cigarette craving in the menthol compared to tobacco session. Primary outcomes: plasma nicotine boost, nicotine area under the curve. Secondary outcome: cigarette craving. Exploratory outcomes: other subjective effects such as liking of e-cig taste. Gender differences will be explored for all outcomes.

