Aim 2: Elucidate the relationship between menthol flavor (vs tobacco flavor) and NMR on nicotine pharmacokinetics and subjective effects during e-cigarette ad libitum use in African Americans who smoke. We hypothesize that participants will take more puffs during the menthol session compared to the tobacco session. Additionally, we hypothesize that participants will titrate their nicotine intake and have similar nicotine plasma levels for both flavor exposure sessions. Furthermore,

we hypothesize that NMR will be positively associated with nicotine delivery (amount of e-liquid used x nicotine e-liquid concentration) for both flavor sessions. Lastly, we hypothesize that participants will have a larger reduction of cigarette craving in the menthol compared to tobacco session. Primary outcomes: plasma nicotine boost, nicotine area under the curve. Secondary outcomes: measure of nicotine delivered to participant and cigarette craving. Exploratory outcomes: number of puffs and subjective effects. Gender differences will be explored for all outcomes.

2. **Probable Duration of Project:** State the expected duration of the project, including all follow-up and data analysis activities.

2 years

TCORS Menthol Pilot Study

Study	Quarter 1	Quarter 2	Quarter 3	Quarter 4
2 experiment sessions	7 completers	7 completers	8 completers Analyze results.	8 completers Analyze results. Present at conference. Publish

K01 Metabolism Study

I anticipate completing both phases of the study by the end of this 5-year K01 award (funded Sept 2020). I anticipate completing 21 participants per year.

3. **Background:** Describe the background information that led to the plan for this project. Provide references to support the expectation of obtaining useful scientific data.

TCORS Menthol Pilot Study

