Experimental Design Aim 2 focuses on the ad-lib e-cigarette exposure. Saliva NMR will be assessed at intake appointment. For each lab session, 120 min after the directed e-cigarette exposure period (Aim 1) participants will undergo a 60 min ad-lib e-cigarette exposure session. For each lab session, each participant will be exposed to the same JUULpods they were exposed to during the directed e-cigarette exposure period. During the ad-lib e-cigarette period, participants can freely self-administer the e-cigarette. The ad-lib period will be video recorded to record puffing behaviors. E-liquids will be measured before and after the session. Two research assistants will independently code the videotapes for puffing behaviors. Participants will be told that they can stop anytime if they feel uncomfortable. Plasma nicotine levels will be assessed at baseline and 15, 30 and 60 minutes after the start of the ad-lib e-cigarette exposure period. Participants will be told that they can stop anytime if they feel uncomfortable. Smoking cessation materials/programs will be offered at the end of the study. **Independent variables:** sex (male or female), nicotine metabolite ratio, flavor (menthol, tobacco), **Dependent variables:** primary outcomes- plasma nicotine boost and nicotine area

under the curve. Secondary outcomes- measure of nicotine delivered to participant and cigarette craving. exploratory outcomes- number of puffs and subjective effects as mentioned in Aim 1. We will explore gender differences for all outcomes

The JUUL™ and menthol and tobacco JUUL pods™[5%(59mg/ml)] will be used for this study. The JUUL™ is one of the most widely used pod e-cigarette devices^{57,58}. Participants will not be allowed to keep the device.

Figure 1: Study Experimental Design

[figure not shown]

Figure 1 Legend: Depicts the time for each lab session. Participants will undergo two lab sessions. Participants will receive two e-liquid flavors (menthol, tobacco) with a fixed nicotine salt concentration in e-cigs (5%) on two separate days (one flavor condition per session).

Assessments

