24. Urine drug and pregnancy tests: Urine drug screen will assess recent drug use at intake for both studies. If participants test positive for any drugs except marijuana and drugs they are not prescribed at the in-person intake appointment, they will not be paid for the visit and will have the opportunity to reschedule this appointment one time. Urine drug screen assesses benzodiazepines, marijuana, methadone, cocaine, methamphetamine, morphine, MDMA, oxycodone, barbiturates, buprenorphine, amphetamine phencyclidine, methadone metabolites,

tricyclic antidepressants and propoxyphene. We will administer pregnancy tests to all female participants at baseline and every vaping session appointment while they are enrolled in the study. In addition, female enrollees will be verbally asked about their pregnancy risk (such as unprotected sex or a missed menstrual period).

25. Plasma nicotine levels for K01 metabolism study will be assessed using blood samples obtained at baseline and 5, 15, 30, 45, 60 minutes after nicotine exposure during the directed e-cigarette portion and plasma nicotine levels will be assessed using blood samples obtained at baseline and 15, 30, 60 minutes after nicotine exposure during ad-lib session. 60 ml of blood will be drawn at each e-cigarette exposure through insertion of an intravenous catheter during e-cigarette directed administration session (total of 120ml for all laboratory session in study or 8 tablespoons) which is below the IRB guidelines of 450 ml within eight research weeks. We will recommend participants wait at least 4 weeks to donate blood. We will then calculate the nicotine boost and the area under the curve. These levels will be determined using LC/MS techniques through the Yale TCORS Lab and Analytical Core.
26. Amount of nicotine delivered to participants will be assessed for K01 metabolism study. The amount of e-liquid in pods will be measured before and after the ad-lib e-cigarette exposure period. We will then multiply the amount of e-liquid used by the nicotine concentration of the e-liquid (5%) to calculate the amount of nicotine delivered to the participants⁶².

5. Genetic Testing N/A

6. **Subject Population:** Provide a detailed description of the types of human subjects who will be recruited into this study.

TCORS menthol pilot study

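### In K01 Aim 2, ad-lib nicotine boost starts from a baseline that still holds nicotine from the same-flavor directed bout, so it can contradict a true titration hypothesis

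*Combined protocol and SAP*

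**What the plan says.** The relevant text is spread over four places in the combined protocol and SAP.

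- **Section I.1, K01 aims.** Aim 1 expects that "during the menthol exposure session participants will have higher plasma nicotine levels compared to the tobacco flavor exposure session", and that "NMR is negatively associated with nicotine plasma levels during the tobacco flavor exposure sessions". Aim 2 expects that "participants will titrate their nicotine intake and have similar nicotine plasma levels for both flavor exposure sessions". Its hypothesis on the nicotine metabolite ratio (NMR) concerns nicotine delivered, calculated from e-liquid used, and predicts a positive association in both flavor sessions.
- **Section I.4, Experimental Design Aim 2.** On timing, the plan says that "120 min after the directed e-cigarette exposure period (Aim 1) participants will undergo a 60 min ad-lib e-cigarette exposure session", and in each session "each participant will be exposed to the same JUULpods they were exposed to during the directed e-cigarette exposure period". The dependent variables begin with "primary outcomes- plasma nicotine boost and nicotine area" under the curve. On sampling: "Plasma nicotine levels will be assessed at baseline and 15, 30 and 60 minutes after the start of the ad-lib e-cigarette exposure period".
- **Section I.4, Assessments, item 25.** After listing separate baselines for the directed and ad-lib series, the plan says only: "We will then calculate the nicotine boost and the area under the curve". It names no reference sample for boost, gives no correction for nicotine already present, and does not say whether AUC is baseline-subtracted.
- **Section I.13, Statistical Considerations.** The mixed model for both aims has NMR, time within lab, flavor, their interactions, and sex. It has no term for plasma nicotine just before the ad-lib period.

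**The concern.** In a crossover one expects residual effects to be washed out or balanced across conditions. Here they are neither. Menthol ad-lib use always follows a menthol bout and tobacco always follows tobacco, so any flavor difference left over from the directed bout falls entirely into the ad-lib flavor contrast. Randomizing the order of the two days does not help, because the carry-over is within a session.

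The titration hypothesis is about plasma level. Boost is a change from a starting point that Aim 1 itself expects to differ by flavor. If participants stop at the same level from different starting points, the changes must differ. One Aim 2 primary outcome could then speak against titration while the concentrations support it, and the plan has no rule for reading the two together. A lower menthol boost could also be reported as a flavor effect on ad-lib use when it reflects the bout given two hours before.

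**Working it through.** **The plan's own figures.** Section I.13 gives 80% power with 85 participants at two-sided 0.05 for |r| = 0.30 and for a within-subject d = 0.32.
- Correlation, by Fisher z: n = ((1.960 + 0.842)/atanh 0.30)² + 3 = 84.9, so 85. This reproduces.
- Paired t test, d = 0.32, n = 85: power 83.1%. Exactly 80% corresponds to d = 0.307. The stated figure is slightly conservative, and nothing below depends on the gap.

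**The identity.** Let L be the ad-lib level, B the ad-lib baseline and f the fraction of the directed-bout nicotine left at 120 min. Subscripts M and T are menthol and tobacco.
- boost = L − B
- if L_M = L_T, then boost_M − boost_T = −(B_M − B_T) = −f × (Aim 1 menthol minus tobacco difference)

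The sign follows for any f above zero. Example in arbitrary units: directed rise 12 (menthol) and 10 (tobacco), f = 0.5, both titrated to 15. The baselines are 6 and 5, so the boosts are 9 and 10.

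**Size in ng/mL.** The documents give no half-life, expected boost or expected menthol excess, so all three are assumptions, as is single-exponential decay: f = 2^(−120/half-life in min).

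| Half-life | f | Directed boost, tobacco | Menthol excess | Shortfall in menthol ad-lib boost |
|---|---|---|---|---|
| 1 h | 0.25 | 5 | 10% | 5 × 0.10 × 0.25 = 0.1 |
| 2 h | 0.50 | 10 | 20% | 10 × 0.20 × 0.50 = 1.0 |
| 3 h | 0.63 | 15 | 30% | 15 × 0.30 × 0.63 = 2.8 |

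**Chance of a significant result under equal ad-lib levels.** Suppose the paired differences have the same SD in both aims (assumption). The spurious effect is then f × d, where d is the Aim 1 effect. With n = 85 and a paired t test, against a nominal 5%:

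| Aim 1 d | f = 0.25 | f = 0.5 | f = 0.7 |
|---|---|---|---|
| 0.32 | 11% (effect 0.08) | 31% (0.16) | 53% (0.22) |
| 0.50 | 21% (0.125) | 63% (0.25) | 89% (0.35) |

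The last column corresponds to a half-life near 4 h. At 3 h and d = 0.32 the effect is 0.63 × 0.32 = 0.20 and the probability about 45%. At f = 0.1 and d = 0.32 it is 6%. The equal-SD assumption matters: at f = 0.5 and d = 0.32, an ad-lib SD 0.75 or 1.5 times the directed SD gives 49% or 16%.

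**NMR.** Suppose r = −0.30 between NMR and the directed level, ad-lib levels flat in NMR, and level and baseline independent with equal SDs (all assumptions). Then boost correlates with NMR at 0.30 × f/√(1 + f²), which is 0.07, 0.13 and 0.17 for f = 0.25, 0.5 and 0.7. These would be detected 10%, 23% and 35% of the time.

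**AUC.** Take ad-lib baselines of 6 (menthol) and 5 (tobacco), both rising linearly to 15 at 60 min. The unsubtracted AUC over the hour is (6 + 15)/2 = 10.5 against (5 + 15)/2 = 10.0. The residual enters with the opposite sign to boost. Of the three measures, only the 60-min level is equal here.

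**The case against.** The strongest reply is that the plan never says boost is the test of titration. The hypothesis is worded as a plasma level, AUC is also primary, and a model with a time factor fits most naturally to the serial concentrations. Read that way, absolute levels and the ad-lib baseline by flavor are already in the analysis. This is a fair reading and it limits the harm. It does not settle the matter: boost remains a primary outcome of the same aim, and the plan does not say which outcome decides the hypothesis.

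Second, boost is undefined. If it is measured from the sample before the directed bout, after overnight abstinence, equal ad-lib levels give equal boosts on average and this flavor artefact goes away. Boost would then include nicotine from the directed bout and no longer isolate ad-lib intake. The separate ad-lib baseline in item 25 makes the pre-ad-lib sample the likelier reference, but the plan should say so.

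Third, a reader might infer that boost must also differ by NMR through carry-over alone. With assumed half-lives of 1.5 and 3 h and a 10 ng/mL directed boost, 10 × (0.63 − 0.40) = 2.3 ng/mL would separate fast from slow metabolizers who end at the same level. The documents do not support this as a prediction. Titration is hypothesized across flavors, not across NMR; the Aim 1 NMR hypothesis covers tobacco sessions only; and the expected rise in nicotine delivered with NMR could make boost vary with NMR as a real effect.

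Fourth, it is tempting to take the unsubtracted AUC as the safe alternative. The AUC example shows that it is not.

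**Conclusion.** The flavor point stands. With the pre-ad-lib sample as reference, and if Aim 1 and titration both hold, expected ad-lib boost is lower with menthol by the residual fraction times the Aim 1 difference. The same-flavor sequence and the 120-min gap are in the documents, and neither the crossover nor the model as written removes the effect from boost.

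The size is not fixed by the documents. It is about 0.1 to 2.8 ng/mL under the assumed ranges, with 1.0 at the middle values. A reader might infer that Aim 2 will reject its own hypothesis. That goes too far: the result concerns an expected value. At the plan's detectable effect and half-lives of 1 to 3 h, the difference would be significant in roughly 11 to 45% of trials, given equal SDs. It becomes likely only with a larger Aim 1 effect or a larger residual. For NMR, carry-over is a possible confounder of the association with boost and no more. The design is usable, but the outcome definition should be settled before analysis.

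**What to change.** Change the Aim 2 outcome wording and add a little analysis:

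1. Name the sample taken just before ad-lib use as the reference for ad-lib boost.
2. Test the titration hypothesis on the absolute plasma concentration at 60 min of the ad-lib period.
3. Keep boost as a measure of net rise. Analyze it with the ad-lib baseline concentration as a covariate, or report it beside that baseline by flavor and NMR. If the final level does not depend on the baseline, boost falls one-for-one as the baseline rises, and the adjusted flavor contrast is zero, as it should be under titration.
4. State whether AUC0-60 is baseline-subtracted, and that it also contains the residual. Unsubtracted, it tends to make menthol higher, so it is not a carry-over-free test of titration.

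Every sample needed is already scheduled. The cost is a few sentences and one further model or table, with no added visits, blood draws or participants.

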Experimental Design: Aim 1 focuses on the directed e-cigarette administration procedure. Saliva NMR will be assessed at intake appointment and will be a continuous measure in this study^{59,60}. Following overnight abstinence from combustible tobacco products (CO≤10 ppm), African Americans who smoke will participate in a double-blind, counterbalanced and randomized e-cigarette exposure laboratory study where they will receive two e-liquid flavors (menthol, tobacco) with a fixed nicotine salt concentration in e-cigarettes (5%) on two separate days (one flavor condition per session). The directed e-cigarette administration procedure will consist of 1 fixed-puffing bout (puffing bout=10 puffs, 3 sec each puff, 30 sec puff interval) as done previously by my mentor, [name]. Per the procedures conducted by my co-mentor [name] research group^{62,63}, plasma nicotine levels will be assessed at baseline and 5, 15, 30, 45 and 60 minutes after nicotine exposure via e-liquids during the directed e-cigarette administration procedure. Heart rate and blood pressure will be measured at 5, 15 and 30 minutes after the final puff. Participants will rate irritation/harshness, coolness, cigarette craving, e-cigarette craving, liking of e-cig taste, reward/appeal of e-cig, nicotine withdrawal and stimulation at baseline, 5 and 15 min after nicotine concentration exposure. Participants will be told that they can stop anytime if they feel uncomfortable. **Independent variables:** sex (male or female), nicotine metabolite ratio, flavor (menthol, tobacco), **Dependent variables:** primary outcomes- plasma nicotine boost, nicotine area under the curve; secondary outcomes- cigarette craving; exploratory outcomes- reward/appeal of e-cigs, e-cig craving, irritation/harshness, coolness, nicotine withdrawal, stimulation, liking of e-cig taste. We will explore gender differences for all outcomes.

Aim 2: Elucidate the relationship between menthol flavor (vs tobacco flavor) and NMR on nicotine pharmacokinetics and subjective effects during e-cigarette ad libitum use

Eligibility/ Recruitment/Screening: African Americans who participate in Aim 1 will participate in Aim 2.

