1. General Labeled Magnitude Scale (gLMS)(experimental sessions)¹: For TCORS Menthol pilot, gLMS ratings will be obtained 5, 15, 30, 45, and 55 minutes after each puff during lab 1 and lab 2. Participants will rate coolness, irritation/harshness, cigarette and e-cigarette craving using the gLMS which is a category ratio scale with 7 semantic labels: "no sensation", "barely detectable", "weak", "moderate", "strong", "very strong", and "strongest imaginable". The labels are positioned quasi-logarithmically according to their empirically determined semantic magnitudes. The gLMS will be displayed on a monitor via a custom LabView® program, and participants will make their ratings using a mouse. Ratings are numerically transformed and then used for statistical analyses. For the K01 metabolism study will be assess irritation/harshness, coolness, cigarette craving, e-

cig craving at baseline, 5 and 15 min after nicotine exposure during the directed puffing section of lab sessions.

2. Labeled Hedonic Scale (LHS)(experimental sessions)³ : For TCORS Menthol pilot, liking of e-cigarette taste will be assessed 5 min after each flavor exposure using the LHS scale. The LHS is a bipolar scale with "neutral" in the middle and 5 symmetrical semantic labels: "like/dislike slightly", "like/dislike moderately", "like/dislike very much", "like/dislike extremely", "most liked/disliked imaginable", positioned on the scale according to their semantic magnitude. The LHS yields ratio-level data on the magnitude of liking/disliking of sensation equivalent to that produced by magnitude estimation (ME). This scale will also be displayed on a computer screen as above and numerically transformed.

For K01 metabolism study, liking of e-cig taste will be assessed at baseline, 5 min and 15 min after nicotine exposure during the directed puffing section of lab sessions.

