3. E-cig Effects (Adapted from Drug Effects Questionnaire (DEQ⁶¹)(experimental sessions): A modified version of the Drug Effects Questionnaire will be used in which participants will rate acute responses to the e-cig on a 0 to 100 mm scale, from "not at all" to "extremely." 5, 15, 30, 45, and 55 minutes after each puffing, we will assess liking/wanting of drug effects (average of "I feel good e-cig effects", "I want more of that e-cig I received", "I feel the e-cig strength" and "I like the e-cig effect"), stimulant effects (average of "I feel energized" and "I feel high"), and nicotine withdrawal (average of "I feel sleepy", "I feel angry", "I feel irritable", "I am having difficulty concentrating", "I feel restless" and "I feel hungry").

For K01 metabolism study, reward/appeal of e-cigs, nicotine withdrawal and stimulation will be assessed at baseline, 5 and 15 min after nicotine exposure during the directed puffing section of lab sessions.

4. Carbon Monoxide (CO) levels (experimental sessions): At intake we will assess recent smoking and participants with ≥ 10 ppm will be included in the study for both studies. For lab sessions for both studies, CO levels in exhaled breath will be measured using a MicroCO breath CO monitor and levels of ≤ 10 ppm will be used to ensure abstinence prior to the experimental sessions.

5. Urine Cotinine levels: At intake for both studies, urine samples will be assessed with Alere iScreen OFD Cotinine urine test to verify eligibility.

6. Salivary nicotine and cotinine levels for TCORS menthol pilot study(experimental sessions): Saliva nicotine and cotinine levels will be monitored using saliva samples obtained 10 times per session (5 min prior to and 5, 15, 30, 45, and 55 minutes after the onset of puff1, and 5, 15, 30, and 45 minutes after the onset of puff 2). To try to avoid contamination from buccal nicotine, participants will be asked to rinse their mouths prior to providing each sample. These levels will be used for correlational analyses with behavioral measures and will be determined using LC/MS techniques at the core laboratory of the YCSTP.

7. Saliva nicotine metabolite ratio or NMR (trans 3'-hydrocotinine/ cotinine) for K01 metabolism study will be assessed through Yale TCORS. To try to avoid contamination from buccal nicotine, participants will be asked to rinse their mouths prior to providing each sample

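### K01 Aim 2 makes cigarette craving an ad-lib outcome with a directional hypothesis, but the written schedule gives no ad-lib time for craving or for any other Aim 1 subjective rating

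*Combined protocol and SAP*

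**What the plan says.** Each K01 session has a directed puffing bout, "followed by 2 hours of abstinence, then 60 minutes of ad libitum e-cigarette use" (Section I.1). Aim 1 covers the directed bout and Aim 2 the ad-lib hour.

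The Aim 2 title in Section I.4 refers to "NMR on nicotine pharmacokinetics and subjective effects during e-cigarette ad libitum use". Its outcome list reads "Secondary outcomes- measure of nicotine delivered to participant and cigarette craving. exploratory outcomes- number of puffs and subjective effects as mentioned in Aim 1". Section I.1 gives Aim 2 its own craving hypothesis, in the same terms as Aim 1: "we hypothesize that participants will have a larger reduction of cigarette craving in the menthol compared to tobacco session".

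The rating schedule is in the Assessments list of Section I.4:

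- Item 1 (gLMS, the craving scale) names cigarette craving among the K01 ratings, and its K01 sentence ends "cig craving at baseline, 5 and 15 min after nicotine exposure during the directed puffing section of lab sessions".
- Item 2 (LHS) says that liking of e-cigarette "taste will be assessed at baseline, 5 min and 15 min after nicotine exposure during the directed puffing section of lab sessions".
- Item 3 (DEQ) says that reward/appeal, nicotine withdrawal and "stimulation will be assessed at baseline, 5 and 15 min after nicotine exposure during the directed puffing section of lab sessions".

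The same list does give ad-lib times for other measures. Under item 25, "plasma nicotine levels will be assessed using blood samples obtained at baseline and 15, 30, 60 minutes after nicotine exposure during ad-lib session". Under item 26, the e-liquid is measured before and after the ad-lib period.

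**The concern.** The outcome list and the measurement schedule do not match. Aim 2 concerns the ad-lib hour, yet the three items that govern the ratings confine them to the directed part of the session. This is hard to read as shorthand, because item 25 states directed and ad-lib times separately for plasma, whereas items 1-3 each name only the directed section.

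If the written items are what staff follow, and Figure 1 adds nothing to them, no ad-lib craving or other Aim 1 subjective rating would exist. Acute ratings cannot be collected afterwards. The Section I.13 mixed model is stated for both aims and has time within lab and flavor as within-subject factors. A larger craving reduction with menthol is a flavor-by-time question in that model, and for Aim 2 there would be no ad-lib time point to enter.

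The reference for reduction in Aim 2 is also unstated. It could be the value just before ad-lib use or the value at the start of the session after overnight abstinence.

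**Working it through.** No sample-size or power figure in the plan bears on this point. The check is a count of stated times and a timeline.

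**1. Ad-lib time points stated in the text**

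| Measure | Source | Ad-lib times | Count |
|---|---|---|---|
| Plasma nicotine | Aim 2 paragraph; item 25 | baseline, 15, 30, 60 min | 4 |
| E-liquid amount | Aim 2 paragraph; item 26 | before, after | 2 |
| Cigarette craving | item 1 | none | 0 |
| Each Aim 1 exploratory rating | items 1-3 | none | 0 |

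I take the plasma baseline here to be the draw before ad-lib use. Puffing is coded from video of the ad-lib hour and needs no rating time. The Aim 1 exploratory ratings are seven: reward/appeal, e-cigarette craving, irritation/harshness, coolness, withdrawal, stimulation and liking of taste. By contrast, craving has 3 written times per session in the directed part (baseline, 5 and 15 min).

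**2. Can the directed ratings stand in for ad-lib ones?**

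Inputs: last rating 15 min after exposure (item 1); ad-lib starts 2 hours after the bout (Section I.1); bout of 10 puffs of 3 sec at 30-sec intervals.

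- Length of bout: 9 × 30 + 3 = 273 sec (4.6 min) if the interval runs from puff start to puff start; 10 × 3 + 9 × 30 = 300 sec (5.0 min) if it is the gap between puffs.
- Gap, counting the 15 min from the last puff: 120 − 15 = 105 min.
- Gap, counting it from the first puff: 120 + 4.6 − 15 = 109.6 min, or 120 + 5.0 − 15 = 110 min.

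The last written rating therefore precedes ad-lib use by about 105 to 110 min and its end by about 165 to 170 min (adding 60). A rating taken before the exposure cannot measure its effect.

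**3. Do other self-reports fill the gap?** Fatigue, shortness of breath and the health checklist are collected at all appointments (items 9, 10 and 13). None measures craving or the other Aim 1 ratings.

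**4. Size of the full rating set, for costing.** gLMS: coolness, irritation/harshness, cigarette craving, e-cigarette craving = 4. LHS: 1. DEQ (item 3): 4 liking/wanting + 2 stimulant + 6 withdrawal = 12. Total 4 + 1 + 12 = 17 items per time point.

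**The case against.** The strongest objection is Figure 1. It follows the Aim 2 paragraph, and its legend says that it sets out the timing of each lab session. I could not see it. A reader might infer from items 1-3 that the trial will take no ad-lib craving ratings. The documents do not support that: they show only that the written text states no time. If the figure marks ad-lib ratings, the point reduces to a conflict between the figure and items 1-3, which still has to be reconciled. This objection stands, and it makes every consequence conditional.

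Second, the Aim 2 list refers back to the Aim 1 subjective effects, so a reader might carry the 5- and 15-minute times over to the ad-lib exposure. This is the weaker reading. The reference is attached to the exploratory effects and not to craving, and items 1-3 expressly tie the times to directed puffing. It does suggest loose drafting more than a deliberate omission.

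Third, the hypothesis compares sessions, so Aim 2 might be thought to reuse the directed ratings. But the hypothesis is stated separately for each aim, and even a whole-session reading needs at least one rating after ad-lib use.

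Finally, a reader might infer that Aim 2 as a whole is compromised. It is not. Its primary outcomes (plasma nicotine boost and area under the curve), nicotine delivered and puff counts all have stated ad-lib measurement, and Aim 1 craving is fully scheduled.

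**Conclusion.** The mismatch is real on the written text. Aim 2 has a secondary outcome with a directional hypothesis, and seven exploratory ratings, for which no ad-lib time is stated. Unless Figure 1 supplies the times, following the written items yields 0 ad-lib craving ratings and the Aim 2 craving hypothesis cannot be tested.

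Severity is minor to should-fix, depending on Figure 1: minor if the figure shows ad-lib ratings and only the wording must be brought into line, should-fix if it does not. Either way this is a cheap improvement. The conclusion assumes that staff work from items 1-3 where nothing else directs them, and that the 2 hours of abstinence run from the end of the bout.

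**What to change.** Check Figure 1 first. Then amend Assessments items 1-3 and the Aim 2 paragraph so that all three agree:

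- Add a gLMS cigarette craving rating at the existing ad-lib baseline and 60-minute blood draws in both sessions.
- Name in advance the one baseline that defines craving reduction for Aim 2. The pre-ad-lib value isolates the ad-lib hour, but it follows 10 directed puffs of the same flavor, which may already have shifted it. The abstinent session baseline, already scheduled in item 1, captures directed and ad-lib use together. These answer different questions, so a result from the other baseline should be reported as a separate question and not as a sensitivity analysis.
- Add the remaining gLMS, LHS and DEQ items at the same two times only if those exploratory outcomes are kept.

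If no ad-lib ratings are intended, remove craving and subjective effects from Aim 2.

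Cost: a short amendment and no added visits or blood draws. Craving alone needs 2 ratings × 2 sessions = 4 single-item ratings per participant. The full set needs 17 items × 4 time points = 68 per participant. There is a small chance that a rating before use primes puffing, which would affect nicotine delivered and also the ad-lib plasma boost and area under the curve. The rating would be given in both flavor sessions alike; the documents do not show whether any such effect would cancel in the flavor comparison.
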